### **5.2.2. Supply, Packaging, and Labeling**

Itacitinib tablets and capsules will be provided to sites in high-density polyethylene bottles as applicable by Incyte. No preparation is required.

All Incyte investigational product labels will be in the local language and will comply with the legal requirements of each country and will state for clinical use only.

### **5.2.3. Storage**

Itacitinib should be stored at ambient conditions (15°C to 30°C, or 59°F to 86°F) as per the [itacitinib IB](#).

### **5.2.4. Instruction to Subjects for Handling Itacitinib**

The subject (parent or legal guardian) must be instructed in the handling of itacitinib as follows:

- To store the bottles at room temperature, in a safe place and out of the reach of children.
- To only remove the number of tablets or capsules needed at the time of administration.
- Not to remove tablets or capsules in advance of the next scheduled administration.

- To make every effort to take doses on schedule.
- To report any missed doses.
- To take tablets or capsules with a glass of water.
- Not to take another dose if vomiting occurs after taking study medication.
- To refrain from taking study medication on the day of clinic visits until after blood samples are collected.
- To fast on PK assessment days (Days 1, 7, and 28 in Phase 1 and Day 7 in Phase 2) before dose administration. Subjects should not consume food 2 hours before dosing until 1 hour after dosing.
- To bring all used and unused bottles of study medication to the site at each visit.

### **5.3. Background Treatment (Corticosteroids)**

Either oral prednisone or intravenous methylprednisolone may be used to begin corticosteroid treatment at the investigator's discretion.

#### **5.3.1. Prednisone**

##### **5.3.1.1. Description**

Prednisone is a white to off-white, odorless, crystalline powder. Tablets are typically white in color and contain lactose monohydrate, magnesium stearate, microcrystalline cellulose, pregelatinized starch, and sodium starch glycolate. Commonly available dose strengths include 1, 2.5, 5, 10, 20, and 50 mg tablets.

##### **5.3.1.2. Supply, Packaging, and Labeling**

Investigators are responsible for ensuring that subjects receive commercially available supplies of prednisone for the duration of the study treatment period. Incyte may provide prednisone where required by applicable law or regulation.

##### **5.3.1.3. Storage**

Prednisone tablets should be stored in accordance with local prescribing information requirements.

#### **5.3.2. Methylprednisolone**

##### **5.3.2.1. Description**

Methylprednisolone sterile powder is an anti-inflammatory glucocorticoid, which contains methylprednisolone sodium succinate as the active ingredient. Methylprednisolone sodium succinate, USP, is the sodium succinate ester of methylprednisolone, and it occurs as a white, or nearly white, odorless hygroscopic, amorphous solid. It is very soluble in water and in alcohol; it is insoluble in chloroform and is very slightly soluble in acetone.

### **5.3.2.2. Supply, Packaging, and Labeling**

Investigators are responsible for ensuring that subjects receive commercially available supplies of methylprednisolone for the duration of the study treatment period. Incyte may provide methylprednisolone where required by applicable law or regulation.

### **5.3.2.3. Storage**

Methylprednisolone (unreconstituted product or solution) should be stored in accordance with local prescribing information.

### **5.3.3. Starting Dose and Administration of Corticosteroids**

All subjects will receive methylprednisolone 2 mg/kg IV daily (or prednisone equivalent) or at a dose that is appropriate for the severity of disease as outlined per local treatment guidelines ([Martin et al 2012](#), [Ruutu et al 2014](#)) as background treatment. Subjects who previously began corticosteroid therapy at a different dose may remain on that dose if considered clinically appropriate by the treating physician. Corticosteroids should be tapered as tolerated per institutional guidelines at a rate that is commensurate with resolution of GVHD manifestations.

If GVHD flares during the taper of prednisone or methylprednisolone, the dose may be re-escalated at the investigator's discretion and will not be considered treatment failure, as long as the dose does not exceed the initial starting dose. If the dose required exceeds this threshold, or if the flare is not responsive to increased corticosteroids or multiple flares are observed, then the subject will be considered to have experienced treatment failure and be withdrawn from study treatment.

## **5.4. Prophylactic and Supportive Care Medications**

Patients who undergo allo-HSCT are at risk for a variety of infections based on the degree of immunosuppression induced by the conditioning regimen before transplant. As such, it is considered routine practice to use antibiotics, anti-infectives, and immunizations as prophylactic therapies ([Tomblyn et al 2009](#)). In cases where post-transplant anti-infective prophylaxis measures are necessary, ongoing therapy may continue at the investigator's discretion per institutional guidelines.

Systemic and topical GVHD prophylaxis medications (eg, cyclosporine, methotrexate, tacrolimus) may be continued at therapeutic doses as appropriate based on stage and sites of disease.

Additional supportive care measures (eg, use of antimotility agents for diarrhea management, beclomethasone, ursodiol) are permitted at the investigator's discretion.

See Section [5.7.4](#) for additional details.

## **5.5. Treatment Compliance**

Treatment compliance with all study-related medications should be emphasized to the subject (parents or legal guardians) by the site personnel, and appropriate steps should be taken to optimize compliance during the study. Itacitinib compliance will be calculated, by the sponsor, based on the drug accountability documented by the site staff and monitored by the

sponsor/designee (tablet counts). Subjects (parents or legal guardians) will be instructed to bring all study-related medications with them to each study visit in order for site personnel to conduct tablet counts to assess study drug accountability. The drug accountability documentation will be used by the sponsor to calculate treatment compliance.

Although commercial supplies of corticosteroids will be used, dose changes and interruptions will also be documented in the medical record and monitored by the sponsor or its designee. As corticosteroid dose strengths and administration types will vary, compliance with corticosteroids will not be calculated.

## **5.6. Treatment Interruptions and Adjustments**

### **5.6.1. Dose Modifications**

Potential dose modifications might be based on both safety and PK data. If the initial itacitinib is not deemed safe and tolerated at each dose level, then a lower dose will be explored (ie, ~50% dose reduction). In case of toxicity, dose modifications at any timepoint will be allowed. Dose modifications might also be based on PK data. Dose interruptions and modifications may occur for individual study subjects based on the emergence or resolution of toxicity.

### **5.6.2. Dose-Limiting Toxicity**

A DLT will be defined as the occurrence of any of the toxicities meeting criteria for DLT as defined below, occurring up to and including Day 28, except those with a clear alternative explanation (eg, disease progression) or transient ( $\leq 72$  hours) abnormal laboratory values without associated clinically significant signs or symptoms based on investigator determination. All DLTs will be assessed by the investigator using CTCAE v4.03 criteria.

Individual subject dose reductions may be made based on events observed at any time during treatment with study drug; however, for the purposes of determining the safe and tolerated dose of itacitinib in combination with corticosteroids, decisions will be made based on events that are observed from the first day of study drug administration through and including Day 28. A lower recommended dose may subsequently be determined based on relevant toxicities that become evident after Day 28.

In order to be included in the tolerability review, subjects must have received the cohort-specific dose of itacitinib for at least 75% of the days (ie, 21 days) during the 28-day surveillance period or have experienced a DLT. At each age-specific cohort, additional subjects may be enrolled to achieve a minimum cohort size of approximately 10 subjects, should discontinuation/withdrawal or dose interruptions/reductions result in a subject being nonevaluable. All safety information, including the AE data from the replaced subjects, will be reviewed during the dose tolerability review process.

A DLT is defined as any of the following:

- Grade 4 neutropenia lasting more than 7 days or a  $\geq 90\%$  decrease in ANC from baseline that can reasonably be attributed to study treatment.
- Platelet count  $< 10 \times 10^9/L$  that can be reasonably attributed to study treatment, and does not recover to  $\geq 20 \times 10^9/L$  after 2 weeks. Recovery is defined as platelets  $\geq 20 \times 10^9/L$  in the absence of platelet transfusion in the 7 days preceding the platelet

recovery date. In case the platelet count was  $< 20 \times 10^9/\text{L}$  at baseline, they should at least reach the baseline level.

- Secondary graft failure, defined as  $> 95\%$  recipient cells any time after engraftment with no signs of relapse, or retransplantation because of secondary neutropenia ( $< 0.5 \times 10^9/\text{L}$ ) and/or thrombocytopenia ( $< 30 \times 10^9/\text{L}$ ; [Olsson et al 2013](#)).
- Any Grade  $\geq 3$  nonhematologic toxicity that can be reasonably attributed to study treatment.  
Any Grade  $\geq 3$  nonhematologic toxicities that may be related to underlying GVHD (eg, nausea, vomiting, diarrhea, rash) will not be considered as DLTs.
- Any Grade  $\geq 3$  clinical chemistry laboratory abnormalities that are considered clinically significant that can reasonably be attributed to study treatment. Transient ( $\leq 72$  hours) abnormal laboratory values without associated clinically significant signs and symptoms and not leading to hospitalization will not be considered as DLTs.
- Any toxicity that can be reasonably attributed to study treatment and leading to treatment discontinuation for more than 2 weeks.

Subjects will be monitored according to Section [9.8](#).

In all cases, investigators are free to employ any measures or concomitant medications, after discussion with the sponsor, necessary to optimally treat the subject.

#### **5.6.2.1. Follow-Up of Dose-Limiting Toxicities**

Any DLT should be followed until it resolves to baseline or appears to have stabilized for a minimum of 4 weeks. During follow-up, subjects should be seen as often as medically indicated to ensure safety.

#### **5.6.3. Criteria and Procedures for Dose Interruptions and Modifications of Itacitinib**

If the drugs need to be interrupted due to toxicity, subjects should be evaluated on a weekly basis until resolution/improvement of the AE. Subjects may resume treatment if no medical condition or other circumstance exists that, in the opinion of the investigator, would make the subject unsuitable for further participation in the study. Treatment with itacitinib may be delayed up to 14 days to allow for resolution of toxicity. The investigator should contact the sponsor medical monitor to discuss cases where treatment has been delayed for more than 14 days before restarting treatment.

Because subjects may enter the study with compromised bone marrow function, these dose reductions are provided as guidelines (see [Table 3](#) and [Table 4](#)); individual decisions regarding dose reduction should be made using clinical judgment and an individual benefit/risk assessment, taking into account relatedness of the AE to the study drug and the subject's underlying condition. Adverse events that have a clear alternative explanation or transient ( $\leq 72$  hours) abnormal laboratory values without associated clinically significant signs or symptoms may be exempt from dose-reduction rules.

The starting dose in each cohort may be reduced based on toxicity (ie, approximately 50% of the initial dose in each cohort). The dose might also be modified based on PK data. Subjects who

are unable to tolerate itacitinib at the reduced dose (50% decrease of the initial dose in each cohort) should be withdrawn from study treatment. The sponsor's medical monitor may be consulted for advice.

**Table 3: Guidelines for Interruption and Restarting of Itacitinib**

ADVERSE EVENT	ACTION TAKEN
Chemistry	

 
AST and/or ALT <math>> 3.0 \times \text{ULN}</math>
 
	
 
Interrupt for up to 14 days until the toxicity has resolved to <math>\leq</math> Grade 1. Exceptions require sponsor approval.
 
Restart at previous dose. If assessed as related to itacitinib, restart at next lower dose and monitor as clinically indicated.
 

 
Total bilirubin elevations that occur in the presence of GVHD response that cannot be attributed to new liver GVHD or concomitant therapy.
 
	
Total bilirubin <math>3.0\text{-}5.0 \times \text{ULN}</math>:
 
 
Reduce dose by 1 level and repeat assessment within 7 days. If elevation persists: 
 
Interrupt until bilirubin <math>\leq 1.5 \times \text{ULN}</math>.
 
Monitor LFTs weekly or more frequently as appropriate.
 
Resume previous dose if resolved in 14 days; if <math>> 14</math> days, maintain reduced dose.
 
 
 
 
Total bilirubin <math>> 5.0\text{-}10.0 \times \text{ULN}</math>:
 
 
Interrupt and repeat assessment within 7 days. If elevation persists: 
 
Keep interruption until bilirubin <math>\leq 1.5 \times \text{ULN}</math>.
 
Monitor LFTs weekly or more frequently as appropriate.
 
Resume previous dose if resolved in 14 days; if <math>> 14</math> days, resume at reduced dose.
 
 
 
 
Total bilirubin <math>> 10.0 \times \text{ULN}</math>:
 
 
Interrupt and repeat assessment within 7 days. If elevation persists: 
 
Keep interruption until bilirubin <math>\leq 1.5 \times \text{ULN}</math>.
 
Monitor LFTs weekly or more frequently as appropriate.
 
Resume at reduced dose if resolved in 14 days; if <math>> 14</math> days, discontinue treatment and monitor as appropriate.
 
 
 


 
Total bilirubin elevations that occur in subjects with Stage 1/2 liver GVHD that cannot be attributed to worsening liver GVHD or concomitant therapy.
 
	
Total bilirubin <math>> 3.0 \times \text{ULN}</math>:
 
 
Repeat assessment within 7 days. If elevation persists: 
 
Reduce dose by 1 dose level.
 
Resume previous dose if bilirubin <math>\leq 3.0 \times \text{ULN}</math>.
 
 
 

Hematology	

 
<math>\text{ANC} < 0.5 \times 10^9/\text{L}</math>, suspected as unrelated to study treatment (eg, GVHD, active cytomegalovirus viremia).
 
	
 
Reduce dose by 1 dose level.
 
Monitor ANC count as clinically indicated.
 
Resume previous dose if ANC count is <math>\geq 0.5 \times 10^9/\text{L}</math> for more than 7 days.
 

 
<math>\text{ANC} < 0.5 \times 10^9/\text{L}</math>, suspected as related to study treatment.
 
	
 
Interrupt for up to 14 days.
 
Monitor ANC count as clinically indicated.
 
Resume at a reduced dose if ANC count is <math>\geq 0.5 \times 10^9/\text{L}</math> for more than 7 days. If the subject's ANC count remains at <math>\geq 0.5 \times 10^9/\text{L}</math> for more than 7 days after resuming treatment at a lower dose, the previous dose may be resumed.
 

**Table 3: Guidelines for Interruption and Restarting of Itacitinib (Continued)**

ADVERSE EVENT	ACTION TAKEN
Hematology (continued)	
• Platelet count is $< 10 \times 10^9/L$ , or platelet count has decreased by $\geq 50\%$ from baseline, suspected as unrelated to study treatment.	
 
• Reduce dose by 1 dose level.
 
• Monitor platelet count as clinically indicated.
 
• Resume at previous dose if platelet count returns to <math>\geq 20 \times 10^9/L</math> for more than 7 days.
 

• Platelet count is $< 10 \times 10^9/L$ , or platelet count has decreased by $\geq 50\%$ from baseline, suspected as related to study treatment.	
 
• Interrupt for up to 14 days.
 
• Monitor platelet count as clinically indicated.
 
• Resume at a reduced dose if platelet count returns spontaneously (without transfusion support) to <math>\geq 20 \times 10^9/L</math> for more than 7 days or within 75% of baseline value. If the subject's platelet count remains at <math>\geq 20 \times 10^9/L</math> without transfusion support for an additional 7 days, the previous dose of study drug may be resumed.
 

Other toxicities	
• Any Grade 1 or Grade 2 toxicity.	
 
• Continue treatment and manage the toxicity.
 
• Monitor as clinically indicated.
 

• Any Grade 3 toxicity, if clinically significant and not manageable by supportive care.	
 
• Interrupt up to 14 days until toxicity resolves to <math>\leq</math> Grade 1.
 
• Restart at same dose; if assessed as related to itacitinib, restart at next lower dose and monitor as clinically indicated.
 

• Any recurrent Grade 3 toxicity at 100 mg QD dose.	
 
• Discontinue study treatment; follow-up per Protocol. Exceptions require sponsor approval.
 

• Any other Grade 4 toxicity.	
 
• Discontinue study treatment; follow-up per Protocol.
 

ALT = alanine aminotransferase; ANC = absolute neutrophil count; AST = aspartate aminotransferase; GVHD = graft-versus-host disease; LFT = liver chemistry test; QD = once daily; ULN = upper limit of normal.

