**Table 4: Potential Dose Reduction and Increase Levels for Itacitinib**

Current Dose	First Dose Reduction	Second Dose Reduction
Initial dose for each cohort disclosed in Section 5.2.1	50%	Discontinue

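### Table 3 stops itacitinib for recurrent Grade 3 toxicity at a fixed 100 mg QD, which is the reduced dose in Cohort 1 only and conflicts with the 50 mg step-down in Cohort 2

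*Combined protocol and SAP*

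**What the plan says.** Under the other toxicities in Table 3, two adjacent rows deal with Grade 3 events.

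- The first covers "Any Grade 3 toxicity, if clinically significant and not manageable by supportive care". Treatment is interrupted for up to 14 days and then restarted "at same dose; if assessed as related to itacitinib, restart at next lower dose and monitor as clinically indicated".
- The second covers "Any recurrent Grade 3 toxicity at 100 mg QD dose". The action is to discontinue, with the rider "Exceptions require sponsor approval".

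Table 4 defines the dose levels relative to the cohort. Its starting point is "Initial dose for each cohort disclosed in Section 5.2.1", the first reduction is 50%, and the second is discontinuation. Section 5.6.3 adds that subjects "unable to tolerate itacitinib at the reduced dose (50% decrease of the initial dose in each cohort) should be withdrawn from study treatment", and Section 5.7.1 makes the same failure to tolerate the reduced dose a mandatory reason for withdrawal.

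Section 5.6.3 also sets the status of both tables: "these dose reductions are provided as guidelines". Individual decisions "should be made using clinical judgment and an individual benefit/risk assessment, taking into account relatedness of the AE to the study drug".

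**The concern.** Every other step in the toxicity-reduction scheme is expressed as a fraction of the cohort's own initial dose. This row alone names a milligram amount. A fixed 100 mg can be the correct trigger only in a cohort whose half dose is 100 mg.

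In Cohort 2 the two adjacent rows can both describe the same child and give different instructions: step down to 50 mg, or stop. Followed literally, the recurrence row ends treatment before the reduction that Table 4 grants. The site would then have to rely on judgment, or ask for a sponsor exception, to use a step that the plan already provides. At stake is consistent guidance on when a 6- to 11-year-old comes off study drug.

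**Working it through.** **Inputs.** Initial doses are from Section 5.2.1. The 50% first reduction is from Table 4 and Section 5.6.3. The half doses used as a check are those listed in Section 5.7.5 for potent CYP3A inhibitors. Planned numbers are from Section 4.3.1.

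**Step 1: locate 100 mg in each cohort.** Half dose = 0.5 × initial dose. The row's trigger can be reached only if 100 / initial dose is 1 or less, and it equals the reduced dose only if that ratio is 0.50. For Cohort 5 the largest initial dose is 1.4 mg/kg × 8 kg = 11.2 mg.

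| Cohort | Initial dose QD | Half dose | Half dose in 5.7.5 | 100 mg / initial | What 100 mg is |
|---|---|---|---|---|---|
| 1 | 200 mg | 100 mg | 100 mg | 0.50 | the reduced dose |
| 2 | 100 mg | 50 mg | 50 mg | 1.00 | the starting dose |
| 3 | 50 mg | 25 mg | 25 mg | 2.00 | not reached |
| 4 | 35 mg | 17.5 mg | 17.5 mg | 2.86 | not reached |
| 5 | 1.4 mg/kg (at most 11.2 mg) | 0.7 mg/kg | 0.7 mg/kg | at least 8.93 | not reached |

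The computed half doses reproduce the Section 5.7.5 list in all five cohorts. The row names the reduced dose in one cohort of five.

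**Step 2: follow a Cohort 2 child through the rows.**

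- First Grade 3 event at 100 mg. If it is judged unrelated, the preceding row restarts the child at 100 mg. If it is manageable by supportive care, that row does not apply and the child stays at 100 mg.
- The toxicity recurs at 100 mg and is now related, clinically significant and not manageable. The preceding row gives the next lower dose, which by Table 4 is 0.5 × 100 = 50 mg. The recurrence row gives discontinuation. Both rows fit.
- If instead the first event was related and not manageable, the child is already on 50 mg. A recurrence there does not meet the 100 mg row. If it is again related and not manageable, the preceding row plus Table 4 leads to discontinuation.

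**Step 3: compare Cohort 1.** A related, unmanageable first event takes the child from 200 to 100 mg. For a second such event, the preceding row plus Table 4 and the recurrence row both say discontinue, so there is no conflict.

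**Step 4: bound the size.** About 30 of 150 planned children are in Cohort 2: 30 / 150 = 20%. This is a ceiling. The documents give no rate of recurrent Grade 3 toxicity, so the number affected cannot be estimated.

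**The case against.** The strongest reply is that the conflict is narrow and the plan has ways out. It needs a first event that led to no reduction, followed by a recurrence that is related, clinically significant and not manageable. Section 5.6.3 makes the tables guidelines subject to judgment, including relatedness, and the row itself allows sponsor-approved exceptions. All of this stands, and it limits the harm. It does not make two contradictory instructions agree.

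A second objection concerns the remedy and also stands. Simply substituting each cohort's half dose for 100 mg would apply a stop regardless of relatedness, whereas the preceding row restarts unrelated events at the same dose. That overlap already exists in Cohort 1 at 100 mg and would spread to the other cohorts. The half dose is also reached without toxicity: through the inhibitor rule in Section 5.7.5 (with ketoconazole added by Administrative Change 1) and through the taper in Section 5.6.4. The rewording therefore has to be narrower.

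Three stronger readings are tempting and are not supported:

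- *Cohorts 3 to 5 have no stopping rule.* They do: Section 5.6.3, Table 4 and Section 5.7.1 stop a child who cannot tolerate the reduced dose, and Section 5.6.5 covers unacceptable toxicity.
- *Outside Cohort 1 a stop is missing for unrelated or manageable recurrences.* The plan nowhere shows that these children should stop. The preceding row and the weight that Section 5.6.3 gives to relatedness point at least as much the other way.
- *Cohort 2 children will be wrongly withdrawn, or the DLT count or Day 28 response rate distorted.* Guideline status and the exception mean that no stop is forced, and no event rate is given from which an effect could be derived.

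**Conclusion.** The point holds as an internal contradiction in a dosing rule. The row names the toxicity-reduced dose in Cohort 1 only, gives an instruction in Cohort 2 that competes with the step to 50 mg, and is inoperative in Cohorts 3 to 5. It should be corrected, but its practical reach is small: at most the roughly 30 children planned for Cohort 2, and within that group only those with the sequence of events described.

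The conclusion rests on the current doses. Section 5.2.1 allows dosing to change, with PK/PD-driven changes requiring a substantial amendment. It also rests on reading the row as it is printed, without an implied restriction to Cohort 1. Sample size and the planned analyses are not in question.

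**What to change.** In the recurrence row, replace the reference to 100 mg QD with: *judged related to itacitinib, after a toxicity-driven reduction to 50% of the cohort's initial dose (Table 4)*. At current doses that is 100, 50, 25 and 17.5 mg and 0.7 mg/kg QD for Cohorts 1 to 5. Keep the sponsor-approved exception. A recurrence at 100 mg in Cohort 2 would then fall under the preceding row, with 50 mg available.

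The cost is one table row in the next amendment, with no change to assessments, sample size or analysis. There are two consequences for treatment conduct:

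- In Cohort 1, unrelated recurrences at 100 mg, and related ones at a 100 mg dose reached by taper or inhibitor adjustment, would follow the preceding row and clinical judgment instead of an automatic stop.
- In Cohorts 2 to 5 the row would become operative at the toxicity-reduced dose. Because it says nothing about manageability, it would include related recurrences that supportive care can manage, as it already does in Cohort 1.

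If the sponsor prefers to keep the broader stop in Cohort 1 or to leave the other cohorts unchanged, the minimum fix is to limit the existing row to Cohort 1. That alone preserves the 50 mg step in Cohort 2.
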